#### **9.4. Device Deficiencies**

A device deficiency is defined in accordance with ISO 14155 as “inadequacy of a medical device with respect to its identity, quality, durability, reliability, safety, or performance.” Device deficiencies include malfunctions, use errors, and inadequate labeling.

The number and percentage of subjects with at least one device deficiency, at least one device deficiency that could have led to a serious AE, and at least one device deficiency leading to a serious AE, along with the numbers of these events, will be summarized for the SS. For subjects with at least one device deficiency that could have led to a serious AE, reasons deficiencies could have led to a serious AE will be summarized.

Device Deficiencies will be listed for the SS, sorting by subject number, start date, and end date (placing missing and partial dates first.)

#### **9.5. Injection Site Reaction 30-Day Diary**

ISRs following treatment with dermal fillers include redness, pain after injection, tenderness to touch, firmness, swelling, lumps/bumps, bruising, itching, discoloration, and other specified events. Subjects will maintain a diary record of the presence, location, frequency, severity, and duration of any ISR for 30 days after treatment (initial and Touch-up). An example of the ISR 30-Day Diary is available in Protocol Appendix 2.

The ISR 30-Day Diary will be completed by the subject beginning on the day of treatment within 60 minutes post-treatment and daily for 30 consecutive days. Subjects who receive Touch-up treatment will return the original ISR 30-Day Diary completed from initial treatment to Day 14 visit. A new ISR 30-Day Diary will be provided at Day 14 to subjects receiving Touch-up treatment. The subject will begin using the new ISR 30-Day Diary to capture any ISRs that occur following Touch-up treatment with Day 1 of the new ISR 30-Day Diary completed within 60 minutes post-treatment.

ISRs that persist longer than 30 days (i.e., ongoing at the end of the diary period) will be reported as AEs.

ISR 30-Day Diary entries will be listed for the SS.

[figure not shown]

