### 6.2. Key Definitions

A subject is considered 'entered' into the study after the subject has signed the Informed Consent Form (ICF) and a subject number has been assigned.

A subject is considered 'enrolled' after confirmation of participation eligibility and treatment with the investigational product Juvéderm® VOLIFT™ with Lidocaine has occurred during the study.

Study treatment is defined as initial or touch-up treatment with Juvéderm® VOLIFT™ with Lidocaine.

Baseline is defined as the latest assessment prior to any study treatments for each subject.

Study day will be calculated as (date of event or assessment)-(date of first filler treatment)+1 if the event or assessment was on or after the date of the first filler treatment, and as (date of event or assessment)-(date of first filler treatment) if the event or assessment was before the date of the first filler treatment. The day of first filler treatment is Study Day 1 (Visit 1). If a touch-up treatment is administered, Visits 3, 4, and 5 will be 14 days +/- 3 days later than the visit label and window, e.g. the study day for an assessment at Visit 3 (Day 30) could be 44 +/- 10, rather than 30 +/- 7.

End of study is the last clinical visit an enrolled subject has in this study. For subjects who complete this study, the end of study visit will be their Visit 5; for subjects who drop out early, they will be asked to come back for the last clinical visit for end of study data collection.

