## **9. Safety**

The analysis set used for safety analyses will be the SS. Safety will be assessed on the basis of AE reports and the ISR 30-day diary.

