## **10. Interim Analyses**

An interim analysis will be performed when all patients complete their 6 months visit (or discontinue early). All TFLs detailed in Sections 15 to 17 will be provided using all data available at the time.

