## 17. Index of Listings

Header	Table Number	Name	Analysis Set
16.2		Subject Data Listings	
16.2.1		Discontinued Subjects	
	16.2.1	Subject Disposition	Screened Set
16.2.2		Protocol Deviations	
	16.2.2	Protocol Deviations	Screened Set – Subjects with Protocol Deviations
16.2.3		Subjects Excluded from the Efficacy Analysis	
	16.2.3.1	Inclusion and Exclusion Criteria Not Met	Screened Set - Subjects Who Did Not Meet at Least One Inclusion or Exclusion Criterion
	16.2.3.2	Exclusions from Analysis Sets	Screened Set
16.2.4		Demographic Data	
	16.2.4.1	Demographics	Screened Set
	16.2.4.2	Medical History	Screened Set – Subjects with Medical History
	16.2.4.3.1	Urine Pregnancy Test	Screened Set - Women of Childbearing Potential
	16.2.4.3.2	Perioral Lines Severity Scale (POLSS)	Screened Set
	16.2.4.4	Prior and Concomitant Medications	Screened Set – Subjects with Medications
	16.2.4.5	Prior and Concomitant Procedures	Screened Set – Subjects with Procedures
16.2.5		Compliance and/or Drug Concentration Data (if available) (Note; exposure information will be included in this section)	
	16.2.5	Juvéderm VOLIFT Treatment	Safety Analysis Set
16.2.6		Individual Efficacy Response Data	
	16.2.6.1	Lip Fullness Scale 2 (LFS2)	Full Analysis Set
	16.2.6.2	Oral Commissures Severity Scale (OCSS)	Full Analysis Set
	16.2.6.3	FACE-Q – Satisfaction with Lips Questionnaire	Full Analysis Set
	16.2.6.4.1	Investigator's Assessment of Global Facial Aesthetic Improvement	Full Analysis Set
	16.2.6.4.2	Subject Assessment of Global Facial Aesthetic Improvement	Full Analysis Set
	16.2.6.5.1	Subject's Assessment of Natural Look And Feel of Their Lips	Full Analysis Set
	16.2.6.5.2	Investigator's Assessment of Product Smoothness	Full Analysis Set
	16.2.6.5.3	Investigator Assessment of Dynamic Lip Lines Upon Animation	Full Analysis Set
	16.2.6.6	Facial Photography	Full Analysis Set

[figure not shown]
Header	Table Number	Name	Analysis Set
16.2.7		Adverse Event Listings	
	16.2.7.1	Treatment-emergent Adverse Events	Safety Analysis Set – Subjects with Treatment-emergent Adverse Events
	16.2.7.2	Non-Treatment-emergent Adverse Events	Screened Set – Subjects with Non-Treatment-emergent Adverse Events
	16.2.7.3	Device Deficiencies	Safety Analysis Set – Subjects with Device Deficiencies
	16.2.7.4	ISR 30-Day Diary	Safety Analysis Set

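### The SAP names the injection site reaction (ISR) diary as one of two bases for safety but plans only a listing of it, so no report would tabulate diary-based incidence, severity or duration.

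*SAP*

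**What the plan says.** SAP Section 9 states: "Safety will be assessed on the basis of AE reports and the ISR 30-day diary". SAP 9.5 then describes what the diary collects: "Subjects will maintain a diary record of the presence, location, frequency, severity, and duration of any ISR for 30 days after treatment". This applies after both the initial and the touch-up injection. The section's one planned output is: "ISR 30-Day Diary entries will be listed for the SS". In SAP Section 17 the diary appears once, as Listing 16.2.7.4, titled "ISR 30-Day Diary". It does not appear in the index of tables (Section 15) or the index of figures (Section 16).

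For the interim analysis, SAP Section 10 says: "All TFLs detailed in Sections 15 to 17 will be provided using all data available at the time".

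Device deficiencies are handled differently. SAP 9.4 asks for counts and percentages, "along with the numbers of these events, will be summarized for the SS", as well as a listing.

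On the link between ISRs and AEs, protocol 9.1.7 and SAP 9.5 both say that a reaction still present when the diary period ends is reported as an AE. For subjects who have a touch-up, SAP 9.5 adds: "Subjects who receive Touch-up treatment will return the original ISR 30-Day Diary completed from initial treatment to Day 14 visit". They then start a new diary.

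**The concern.** A subject-level listing does not give a reader an incidence. If the diary is half of the stated basis for safety, one expects at least the number of subjects with each reaction, its worst grade and how long it lasted. The plan provides none of these from the diary.

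The AE tables may not make up the difference. The Directions for Use in protocol Appendix 1 say that post-injection inflammatory reactions can last about a week, and that injection into mucous membrane can bring more swelling and bruising. The reactions most to be expected in a lip study are therefore short ones, which the over-30-days rule does not send to the AE data. Anyone wanting their frequency from the diary would have to count it by hand from the listing, at the interim and again at the end.

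**Working it through.** The plan gives no figure to reproduce here. The check is a count of planned outputs and a comparison of sections.

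**Safety summary tables (SAP Section 15, block 14.3)**
- Treatment-emergent AEs: 14.3.1.1 to 14.3.1.11 = 11
- Device deficiencies: 14.3.1.12 = 1
- Exposure: 14.3.4.1 to 14.3.4.4 = 4
- Total: 11 + 1 + 4 = 16. Tables 14.3.4.2 and 14.3.4.3 repeat 14.3.4.1 for other analysis sets, so 16 − 2 = 14 are distinct.
- The 14.3.2 entries are AE listings and are not counted.

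**Use of the diary:** 0 of 16 tables (0 of 14 distinct), 0 of 1 figure (14.3.4.5 plots volume against FACE-Q), 1 listing. SAP Section 11 records one departure from the protocol, on product compliance, and does not mention the diary.

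**Can the AE tables substitute?**
- Protocol 9.1.7 and SAP 9.5 send ISRs that outlast the diary period to the AE data. Neither says that only those are AEs.
- Pointing to separate streams: protocol 6.2.8 and 8.2 name ISRs and AEs side by side, and protocol 9.2.2 leaves ISR severity to the diary.
- Pointing to overlap: the AE definition in protocol 9.1.1 is broad, protocol 9.2 requires all AEs and device effects to be recorded, and ISRs are defined within the AE chapter.
- Protocol 7.1.7 and Appendix 2, which might decide it, are partly unreadable.
- If short ISRs are not AEs, they reach no table. If they are, SAP 9.3 gives subject counts and maximum severity by preferred term, but on the AE severity scale. No table in the index reports duration.

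**Duration after the initial injection in touch-up subjects.** The first diary is handed in at the Day 14 visit, so it covers about 14/30 = 47% of its intended period. SAP 6.2 says that after a touch-up "Visits 3, 4, and 5 will be 14 days +/- 3 days later than the visit label and window". If that tolerance reflects when the touch-up is given (an inference, because no Visit 2 window is readable), the range is 11/30 = 37% to 17/30 = 57%. A reaction still present then has an unknown full duration in that diary.

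**Would a table be informative?** If all 60 subjects return a diary, the 95% half-width for a proportion p is 1.96 × √(p(1 − p)/60). At p = 0.10 or 0.90 it is 7.6 percentage points, and at p = 0.50 it is 12.7. That is adequate for description.

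**The case against.** The strongest reply is that no commitment is broken. The study has no safety objective, protocol 10.5.4 promises AE summaries only, and basing safety on the diary does not in itself promise a table. The SAP also lists without summarizing elsewhere: perioral line scores and pregnancy tests (7.4), procedures (7.5.3) and photographs (8.1). The different treatment of device deficiencies is a choice, not a contradiction. All of this stands, and it is why the point is a reporting gap. But none of those listed items is named as a basis for safety, and the diary is.

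A reader might go further and infer that the reports will say nothing at all about how many subjects had swelling, bruising or lumps. The documents do not support that. If sites record short ISRs as AEs, the AE tables will count them, and the readable text leaves this open. What is certain is narrower: nothing is tabulated from the diary.

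Redaction is not a sufficient answer. The table shells cannot be read, but SAP 9.5 and the indexes can, and they define the outputs. SAP 6.1 does not help either: it says how a variable is summarized when it is, not which variables are.

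**Conclusion.** The point holds as a reporting gap that should be closed. The diary is one of two named bases for safety, yet it feeds 0 of 16 safety summary tables and 0 of 1 figure, at both the interim and the final analysis. Diary-based incidence, severity and duration would be absent from both reports.

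The wider consequence is conditional. ISRs of 30 days or less would appear in no table unless they are also recorded as AEs. If they are, what is missing reduces mainly to duration and diary-defined severity. This rests on the readable indexes being complete, and it does not depend on any assumed reaction rate or touch-up rate, neither of which the documents give. The number of untabulated diary entries cannot be stated, because the diary form is not readable. It would be wrong to read this as a protocol violation.

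**What to change.** In SAP 9.5 and the index of tables, add Safety Analysis Set tables giving the number and percentage of subjects with each ISR type, by maximum severity and by duration, separately after initial and touch-up treatment. Use subjects with a returned diary for the relevant treatment as the denominator, and show how many that is.

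Show duration after the initial treatment by touch-up status, with ongoing at touch-up as its own category, so that truncated durations are not mixed with complete ones. State how missing diary days are handled. Include the tables in the interim set.

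If the unreadable diary sections do not already settle it, reconcile protocol 9.1.1, protocol 9.1.7 and SAP 9.5 on whether ISRs of 30 days or less are also AEs, so that the diary and AE tables can be read together.

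The cost is a few more descriptive tables from data already collected, one simple missing-day rule and, if needed, a clarifying sentence. No new data collection or change in clinical procedure is involved.

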## **10. Interim Analyses**

An interim analysis will be performed when all patients complete their 6 months visit (or discontinue early). All TFLs detailed in Sections 15 to 17 will be provided using all data available at the time.

## **11. Changes from Analysis Planned in Protocol**

Subject study product compliance was to be summarized using descriptive statistics, but this information was not collected in the database.

This document is [REDACTED]

[figure not shown]
## **12. Reference List**

[figure not shown]
Not applicable.

### 13. Programming Considerations

[figure not shown]
All TFLs, and statistical analyses will be generated [REDACTED]

[REDACTED] Computer-generated TFLs will adhere to the following specifications.

[figure not shown]

[figure not shown]
This document is [REDACTED]

This document is [REDACTED]

This document is [REDACTED]

## **14. Quality Control**

SAS programs are developed to produce output such as analysis data sets, summary tables, data listings, figures or statistical analyses. [REDACTED]

[REDACTED]

[REDACTED]

Quality control is defined here as the operational techniques and activities undertaken to verify that the SAS programs produce the output by checking for their logic, efficiency and commenting and by review of the produced output.

## 15. Index of Tables

Header	Table Number	Name	Analysis Set
14.		Tables, Figures, and Graphs Referred to but not Included in the Text	
14.1		Demographic Data Summary Tables	
14.1.1		Subject Disposition	
	14.1.1	Number of Subjects Enrolled and Study Termination	Screened Set
14.1.2		Protocol Deviations	
	14.1.2.1	Major Protocol Deviations	Full Analysis Set
	14.1.2.2	Reasons for Exclusion from Analysis Sets	Screened Set
14.1.3		Demographic and Baseline Characteristics	
14.1.3.1		Subject Demographic and Baseline Characteristics	
	14.1.3.1.1	Subject Demographic and Baseline Characteristics	Safety Analysis Set
	14.1.3.1.2	Subject Demographic and Baseline Characteristics	Evaluable Set
	14.1.3.1.3	Subject Demographic and Baseline Characteristics	Per Protocol Set
14.1.3.2		Baseline Characteristics	
	14.1.3.2.1	Fitzpatrick Skin Phototype	Safety Analysis Set
	14.1.3.2.2	Fitzpatrick Skin Phototype	Evaluable Set
	14.1.3.2.3	Fitzpatrick Skin Phototype	Per Protocol Set
14.1.3.3		Medical History	
	14.1.3.3	Medical History	Safety Analysis Set
14.1.4		Medications	
	14.1.4.1	Prior Medications	Safety Analysis Set
	14.1.4.2	Concomitant Medications	Safety Analysis Set
14.2		Efficacy Data Summary Tables	
14.2.1		Primary Efficacy Parameter Responder Rate for Lip Fullness on the LFS2	
	14.2.1.1	Primary Efficacy Parameter Responder Rate for Lip Fullness on the LFS2: Primary Analysis	Evaluable Set
	14.2.1.2	Primary Efficacy Parameter Responder Rate for Lip Fullness on the LFS2: Secondary Analysis	Per Protocol Set
14.2.2		Secondary Efficacy Parameters	
	14.2.2.1	Secondary Efficacy Parameter 1 Oral Commissures Severity Scale (OCSS)	Evaluable Set
	14.2.2.2	Secondary Efficacy Parameter 2 FACE-Q – Satisfaction with Lips Questionnaire	Evaluable Set
	14.2.2.3	Secondary Efficacy Parameter 3 Investigator's Assessment of Global Facial Aesthetic Improvement	Evaluable Set
	14.2.2.4	Secondary Efficacy Parameter 4 Subject Assessment of Global Facial Aesthetic Improvement	Evaluable Set

Header	Table Number	Name	Analysis Set
	14.2.2.5	Secondary Efficacy Parameter 5 Subject's Assessment of Natural Look and Feel of Their Lips	Evaluable Set
	14.2.2.6	Secondary Efficacy Parameter 6 Investigator's Assessment of Product Smoothness	Evaluable Set
	14.2.2.7	Secondary Efficacy Parameter 7 Investigator Assessment of Dynamic Lip Lines Upon Animation	Evaluable Set
14.3		Safety Data Summary Tables	
14.3.1		Adverse Events	
	14.3.1.1	Treatment-emergent Adverse Events – Overall Summary	Safety Analysis Set
	14.3.1.2	Treatment-emergent Adverse Events by System Organ Class and Preferred Term	Safety Analysis Set
	14.3.1.3	Treatment-related Treatment-emergent Adverse Events by System Organ Class and Preferred Term	Safety Analysis Set
	14.3.1.4	Procedure-related Treatment-emergent Adverse Events by System Organ Class and Preferred Term	Safety Analysis Set
	14.3.1.5	Serious Treatment-emergent Adverse Events by System Organ Class and Preferred Term	Safety Analysis Set
	14.3.1.6	Serious Treatment-related Treatment-emergent Adverse Events by System Organ Class and Preferred Term	Safety Analysis Set
	14.3.1.7	Serious Procedure-related Treatment-emergent Adverse Events by System Organ Class and Preferred Term	Safety Analysis Set
	14.3.1.8	Treatment-emergent Adverse Events by System Organ Class, Preferred Term, and Maximum Severity	Safety Analysis Set
	14.3.1.9	Treatment-emergent Adverse Events by System Organ Class, Preferred Term, and Maximum Relationship to Study Treatment	Safety Analysis Set
	14.3.1.10	Treatment-emergent Adverse Events by System Organ Class, Preferred Term, and Maximum Relationship to Study Procedure	Safety Analysis Set
	14.3.1.11	Treatment-emergent Adverse Events Leading to Study Discontinuation by System Organ Class and Preferred Term	Safety Analysis Set
	14.3.1.12	Device Deficiencies	Safety Analysis Set
14.3.2		Listings of Deaths, Other Serious and Significant Adverse Events	
	14.3.2.1	Serious Treatment-emergent Adverse Events, Listing	Safety Analysis Set – Subjects with Serious Treatment-emergent Adverse Events

Header	Table Number	Name	Analysis Set
	14.3.2.2	Treatment-related Treatment-emergent Adverse Events, Listing	Safety Analysis Set – Subjects with Treatment-related Treatment-emergent Adverse Events
	14.3.2.3	Procedure-related Treatment-emergent Adverse Events, Listing	Safety Analysis Set – Subjects with Procedure-related Treatment-emergent Adverse Events
	14.3.2.4	Treatment-emergent Adverse Events Leading to Study Discontinuation, Listing	Safety Analysis Set – Subjects with Treatment-emergent Adverse Events Leading to Study Discontinuation
14.3.3	Not to be used for any Tables	Narratives of Deaths, Other Serious and Certain Other Significant Adverse Events (NOTE: Medical Writing narratives only, not completed by Syneos Health Biostatistics)	
14.3.4		Extent of Exposure	
	14.3.4.1	Extent of Exposure	Safety Analysis Set
	14.3.4.2	Extent of Exposure	Evaluable Set
	14.3.4.3	Extent of Exposure	Per Protocol Set
	14.3.4.4	Summary of Total Volume Administered (mL) by Presence or Absence of a Treatment-emergent Adverse Event	Safety Analysis Set

## 16. Index of Figures

Header	Table Number	Name	Analysis Set
14.3.4		Extent of Exposure	
	14.3.4.5	Scatter Plot of Total Volume Administered vs. FACE-Q Score by Visit	Safety Analysis Set

## 17. Index of Listings

Header	Table Number	Name	Analysis Set
16.2		Subject Data Listings	
16.2.1		Discontinued Subjects	
	16.2.1	Subject Disposition	Screened Set
16.2.2		Protocol Deviations	
	16.2.2	Protocol Deviations	Screened Set – Subjects with Protocol Deviations
16.2.3		Subjects Excluded from the Efficacy Analysis	
	16.2.3.1	Inclusion and Exclusion Criteria Not Met	Screened Set - Subjects Who Did Not Meet at Least One Inclusion or Exclusion Criterion
	16.2.3.2	Exclusions from Analysis Sets	Screened Set
16.2.4		Demographic Data	
	16.2.4.1	Demographics	Screened Set
	16.2.4.2	Medical History	Screened Set – Subjects with Medical History
	16.2.4.3.1	Urine Pregnancy Test	Screened Set - Women of Childbearing Potential
	16.2.4.3.2	Perioral Lines Severity Scale (POLSS)	Screened Set
	16.2.4.4	Prior and Concomitant Medications	Screened Set – Subjects with Medications
	16.2.4.5	Prior and Concomitant Procedures	Screened Set – Subjects with Procedures
16.2.5		Compliance and/or Drug Concentration Data (if available) (Note; exposure information will be included in this section)	
	16.2.5	Juvéderm VOLIFT Treatment	Safety Analysis Set
16.2.6		Individual Efficacy Response Data	
	16.2.6.1	Lip Fullness Scale 2 (LFS2)	Full Analysis Set
	16.2.6.2	Oral Commissures Severity Scale (OCSS)	Full Analysis Set
	16.2.6.3	FACE-Q – Satisfaction with Lips Questionnaire	Full Analysis Set
	16.2.6.4.1	Investigator's Assessment of Global Facial Aesthetic Improvement	Full Analysis Set
	16.2.6.4.2	Subject Assessment of Global Facial Aesthetic Improvement	Full Analysis Set
	16.2.6.5.1	Subject's Assessment of Natural Look And Feel of Their Lips	Full Analysis Set
	16.2.6.5.2	Investigator's Assessment of Product Smoothness	Full Analysis Set
	16.2.6.5.3	Investigator Assessment of Dynamic Lip Lines Upon Animation	Full Analysis Set
	16.2.6.6	Facial Photography	Full Analysis Set

[figure not shown]
Header	Table Number	Name	Analysis Set
16.2.7		Adverse Event Listings	
	16.2.7.1	Treatment-emergent Adverse Events	Safety Analysis Set – Subjects with Treatment-emergent Adverse Events
	16.2.7.2	Non-Treatment-emergent Adverse Events	Screened Set – Subjects with Non-Treatment-emergent Adverse Events
	16.2.7.3	Device Deficiencies	Safety Analysis Set – Subjects with Device Deficiencies
	16.2.7.4	ISR 30-Day Diary	Safety Analysis Set

## 18. Shells

[figure not shown]
### 18.1. Table Shells

[figure not shown]
This document is [REDACTED]

[figure not shown]
This document is [REDACTED]

[figure not shown]

[figure not shown]
This document is [REDACTED]

[figure not shown]

This document is [REDACTED]

[figure not shown]

This document is [REDACTED]

[figure not shown]

[figure not shown]
This document is [REDACTED]

[figure not shown]

This document is [REDACTED]

[figure not shown]

[figure not shown]
This document is [REDACTED]

This document is [REDACTED]

[figure not shown]

This document is [REDACTED]

[figure not shown]

[figure not shown]
This document is [REDACTED]

This document is

[figure not shown]
This document is [REDACTED]

[figure not shown]

This document is [REDACTED]

[figure not shown]

[figure not shown]

This document is [REDACTED]

[figure not shown]

This document is [REDACTED]

[figure not shown]

This document is [REDACTED]

[figure not shown]

This document is [REDACTED]

[figure not shown]
This document is [REDACTED]

This document is [REDACTED]

[figure not shown]

This document is [REDACTED]

[figure not shown]

[figure not shown]
This document is [REDACTED]

This document is

[figure not shown]

This document is [REDACTED]

[figure not shown]

This document is [REDACTED]

[figure not shown]
This document is [REDACTED]

[figure not shown]

This document is [REDACTED]

[figure not shown]

[figure not shown]

This document is [REDACTED]

[figure not shown]

This document is [REDACTED]

[figure not shown]

[figure not shown]

This document is [REDACTED]

[figure not shown]

[figure not shown]
This document is [REDACTED]

[figure not shown]

[figure not shown]
This document is [REDACTED]

[figure not shown]

[figure not shown]
This document is [REDACTED]

[figure not shown]
This document is [REDACTED]

[figure not shown]

[figure not shown]
This document is [REDACTED]

[figure not shown]

This document is [REDACTED]

[figure not shown]

This document is [REDACTED]

[figure not shown]

This document is [REDACTED]

This document is [REDACTED]

[figure not shown]
This document is [REDACTED]

[figure not shown]
